PROTOCOL TITLE: Virtual Pediatric Trauma Center

ClinicalTrials.gov – Study Protocol and Statistical Analysis Plan

Title: Improving Family-Centered Pediatric Trauma Care: The Standard of Care Versus the Virtual Pediatric Trauma Center

NCT Number: NCT04469036

Document Date: 09/22/2022

Protocol Title

Title: *Virtual Pediatric Trauma Center*

Protocol Version Date: 2022-09-22

1) Objectives

[figure not shown]
- **Aim #1a:** To compare the parent/family experience of care and distress at 3-days and 30-days following a childhood injury requiring an emergency department visit in a non-pediatric trauma center under the current standard model of care and the VPTC model of care.
 - Null Hypothesis: Measures of parent/family experience of care and measures of distress will be similar between the two models of care.
- **Aim #1b:** To compare the frequency of potentially avoidable transfers (PAT) and transfers in a non-pediatric trauma center under the current standard model of care and the VPTC model of care.
 - Null hypothesis: Frequency of PATs and transfers will be similar between the two models of care.
- **Aim #2:** To compare 30-day healthcare utilization between injured children cared for under the current standard model of care and the VPTC model of care.
 - Null Hypothesis: Hospitalizations, re-hospitalizations, primary and specialty care visits will be similar between the two models of care.
- **Aim #3:** To compare the out-of-pocket costs and financial burdens experienced by parents/families at 3-days and 30-days following a childhood injury requiring an emergency department visit in a non-pediatric trauma center under the current standard model of care and the VPTC model of care.
 - Null Hypothesis: Out-of-pocket costs and financial burdens for parent/families will be similar between the two models of care.

2) Background

The American College of Surgeons Committee on Trauma (ACS-COT) has been committed to improving the care provided to injured patients since 1922. An essential component of their efforts has been the creation of minimum standards for trauma facilities and a tiered trauma care system. As detailed in the ACS-COT published guidelines, *Resources for Optimal Care of the Injured Patient*,¹ these standards outline the five levels of trauma facilities that define varying levels of commitment, readiness, resources, policies, patient care, and performance improvement.¹ A Level I trauma center is the highest designation and is only granted to hospitals that are able to provide the highest level of care to all injured patients. The ACS-COT Trauma Center Verification process has been instrumental in improving outcomes among injured children and adults, and has become the national model of trauma care coordination as well as the prototype for trauma care on an international level.^{2,3}

PROTOCOL TITLE: Virtual Pediatric Trauma Center

While the regionalization of trauma care has resulted in improved outcomes,^{4,5} the **current standard of care** has created disparities in access for patients injured in geographically isolated locations. When children living in remote communities are injured and present to a non-pediatric trauma center emergency department (ED), they are transferred to the regionalized Level I pediatric trauma center.⁶ In more than half of the states in the US, a majority of children live more than 30 miles from a designated Level I pediatric trauma center. Currently, there are *more than 41 million children in the*

Sources: GAO analysis of American Trauma Society and U.S. Census Bureau data (data); Map Resources (map). | GAO-17-334

US that have poor access to care, living more than 30 miles from a pediatric trauma center, and it is these children who would benefit the most from a re-engineered system of care that addresses the disparities in access for injured children.^{7,8}

Because the current regionalization of trauma centers has created disparities in access, many pediatric trauma experts, including health policy makers, health services researchers, and front line clinicians, have advocated for the use of telemedicine so that the Level I pediatric trauma center expertise can be transmitted to the receiving EDs where a majority of pediatric trauma patients initially present.⁹⁻¹² This **newer system of care** has been commonly referred to as the “Virtual Pediatric Trauma Center” (VPTC) and is increasingly used by many hospitals and EDs throughout the country.^{12,13} The VPTC creates a model of care that connects EDs in non-Level I trauma centers using telemedicine to bring expert pediatric trauma care to the bedside of injured children, no matter which hospital the patient presents to first. While this newer model of care enables participation of parents/families in the initial trauma care, there is conflicting and limited literature comparing this model to the current standard of care as it relates to parent/family-experience and distress, healthcare utilization, and financial impact on parents/families.¹⁴

3) Inclusion and Exclusion Criteria

Inclusion

PROTOCOL TITLE: Virtual Pediatric Trauma Center

- Pediatric patients (<18 years old) with an acute injury at the time of a transfer consultation call to UC Davis Trauma Surgery, Orthopedic Surgery, or Neurosurgery from eleven outside emergency departments*
- Parents/guardians of the above patients will be contacted to complete surveys

*Adventist Health Lodi, Adventist Health Rideout, Marshall Medical Center, Mayers Memorial Hospital, Mercy Medical Center Redding, Mercy Methodist Hospital, Mercy San Juan Medical Center, Oroville Hospital, Tahoe Forest Hospital, Woodland Memorial Hospital, Barton Memorial Hospital

Exclusion The following patients will be excluded from recruitment for survey completion but included in the dataset:

- Pediatric patients who are wards of the state
- Pediatric patients who die before the 3-day survey is administered
- Pediatric patients receiving cardiopulmonary resuscitation prior to presentation to either the outside or UC Davis emergency department

4) Study Timelines

Data will be abstracted for all patients with transfer center consultations from eligible emergency departments* between November 30th, 2020 and March 31st, 2024.

Parents/guardians of eligible patients will be contacted within 3-days of the eligible emergency department visit to complete the first survey. They will then be asked to complete surveys at 30-, 60-, and 90-days after the eligible emergency department visit. They will be given until 104 days after the eligible emergency department visit to complete the final survey.

The study team will complete primary analyses by May 31st, 2023.

5) Study Endpoints

Transfer consultation data will be collected until March 31st, 2024.

Surveys will be collected until March 14th, 2023.

6) Procedures Involved

Systems Level Intervention

To compare our parent, family, community and provider informed outcomes between the current standard of care and the VPTC, we will use a prospective stepped-wedge trial design,⁶² which has important advantages over alternative designs. First, with the stepped-wedge design, changes in the quality and standards of pediatric trauma care over time can be accounted for, unlike a simple pre-test, post-test study design where

PROTOCOL TITLE: Virtual Pediatric Trauma Center

changes in care could be confounded by temporal changes and secular trends. Second, in common with a cluster randomized design, and in contrast to patient-randomized designs, our design minimizes contamination bias that could arise among researchers and participants when patients at the same site have been concurrently randomized to two different models of care. In addition, the stepped-wedge design has an important statistical power advantage over a parallel-groups cluster-randomized trial. The latter design suffers a loss of statistical power that arises from within-cluster correlation (ICC), even when ICC is as modest as 5%, a typical value for process-of-care outcomes.⁶³ The presence of positive intra-cluster correlation has the opposite effect in a stepped-wedge design, because in that design, the contrast of interest is a “within-cluster” contrast, so that the cluster serves as its own control, increasing the effective sample size and resulting statistical power.⁶⁴

After a six-month pre-implementation period, the study will begin with all hospitals beginning in the standard of care condition and with patients enrolled for 13 consecutive 8-week periods. At the end of each of the 8-week periods, one hospital ED will switch to the VPTC model of care condition, according to its randomly assigned enumeration. Following the 2-year (13 x 8 weeks) data collection period, there will be a six-month post-implementation period for data analysis and dissemination.

Stepped-Wedge Trial Design:

Hospital	6-Month Period	8-Week Periods													6-Month Period	
		Pre-Implementation	Standard of Care	One of ten hospitals is randomized to VPTC according to stratification										Full VPTC	Data Analysis	
	1	2	3	4	5	6	7	8	9	10	11	12	13	14	15	
1																
2																
3																
4																
5																
6																
7																
8																
9																
10																

Of note, after starting the study, one of the hospitals declined to further participate and will be replaced by another similar hospital. The replacement protocol has been approved by the senior statistician on the project.

In order to ensure that we can fully evaluate this **systems level intervention** we will abstract the following variables from the UC Davis EMR: Sending hospital, Glasgow Coma Score (GCS) at time of consultation & at time of departure from OSH, encounter number, outcome of the transfer center call, time of transfer call, reasons for transfer, which trauma/ortho/neuro/other specialist took call, mode of transport, length and frequency of OR visit, ICD-10-CM/PCS codes, CPT codes, Epic imaging order codes, admitting service, critical care use, specific UCD provider completing telehealth visit, type of primary service admitted, disposition, location and time of discharge; Patient characteristics: MRN, patient name, age,

PROTOCOL TITLE: Virtual Pediatric Trauma Center

race/ethnicity, sex, language, insurance, parent/guardian phone/e-mail, home address

Parent/Guardian Survey

Parents/guardians of patients from above will be approached either by StudyPages, phone, e-mail, or in-person and asked to complete surveys (either electronic, via REDCap, or phone (entered directly into REDCap by a study team member)) at 3-, 30-, 60-, and 90-days after the after the eligible emergency department visit.

The surveys will contain no identifying information and are attached in IRBNet.

The primary risk to this study is loss of confidentiality. All information will be stored in REDCap, StudyPages, or in password protected databases on secure UC Davis servers.

Retrospective Data Entry

Upon approval of 3/18/2021 protocol version, Barton Memorial Hospital patients will be entered into REDCap dating back to 11/30/2020. Depending on the patient's survey timeline, research staff will recruit patients to complete their prospective 3-, 30-, 60-, 90- day surveys.

7) Data and/or Specimen Management and Confidentiality

- I understand that if this study involves the use of the UC Davis Health Electronic Health Record (EMR/EPIC) also contains the clinical data for Marshall Medical Center (MMC). I understand that MMC patient data cannot be accessed for research purposes and that I must take the necessary steps to ensure that MMC data is not accessed, used, or disclosed for UC Davis Health research purposes.
- I understand that if this study involves use of UC Davis students' educational records (including records in the PI's own possession such as course exams/assignments), I must consult with the Registrar's office to see if all requirements of the Family Educational Rights and Privacy Act (FERPA) are satisfied.

This study is evaluating a systems-level intervention; a system-level intervention means that we are doing an intervention on how we deliver healthcare. In other words, our intervention is a test of change to the healthcare system. Because we are doing a systems level intervention, we need to evaluate outcomes on all the eligible patient transfer consultations. Our outcomes include transfers and potentially avoidable transfers. We therefore need to know if all the transfers, among our eligible patients were "avoidable or potentially avoidable" or not. The outcome data (and our research study) would be not useful if we can only gather data the patients who were consented. It is not feasible to get consent from every patient's parent.

Doing a systems intervention and only evaluating the outcomes on the patients who return a HIPAA authorization would make the study not valid. It is therefore not possible

PROTOCOL TITLE: Virtual Pediatric Trauma Center

to do the research without the waiver, because a systems intervention study requires evaluating the outcomes on all the patients involved in order to be valid.

In summary, rationale for the waiver of HIPAA and waiver of consent for the data abstraction include: (1) The use or disclosure of protected health care information involves no more than minimal risk; (2) the research could not practicably be conducted without the waiver or alteration; and (3) the research could not practicably be conducted without access to and use of the PHI.

All study personnel involved in this proposed project have received Human Subjects Protection and HIPAA education.

Data Analysis Plan/Statistical Procedures:

Regression analyses will be conducted within a generalized linear mixed model framework for multilevel data (patients nested within hospitals), with random effects for hospitals specified to account for unmeasured sources of between-unit heterogeneity.⁶⁵⁻⁶⁷ A within-site time-varying binary indicator (VPTC vs. standard of care) will be included in the model to permit estimating the key contrasts of interest. For linear-normal mixed models (e.g., experience of care and distress), effect sizes will be adjusted mean differences; for binary and count outcomes fitted with logistic and Poisson regression models, respectively, effect sizes will be adjusted odds and rate ratios, respectively. For outcomes assessed at both 3-days and 30-days after injury, we anticipate estimating time point-specific contrasts of the VPTC vs. standard of care groups. To do this, models will also include a binary indicator for time point (3 day vs. 30 day) as well as interactions of time point with the time-varying treatment group indicator. Additional independent variables will include a parsimonious and pre-specified set of patient-level effects to account for study design effects and to improve the precision of estimated effects, accounting for known sources of heterogeneity.^{66,68,69} To account for confounding by calendar time in our stepped-wedge design,⁶² we will compute each patient's date at enrollment in the study and use fractional polynomial modeling to determine the order of polynomial (linear, quadratic, cubic, etc.) to specify the calendar date of enrollment effects, to account for temporal effects.⁷⁰ A senior health economist will conduct the economic analyses relevant to the financial burdens experienced by parent/family members. Additional details for each aim and outcome are provided below.

8) Data and/or Specimen Banking

N/A

9) Provisions to Monitor the Data to Ensure the Safety of Subjects

N/A

10) Withdrawal of Subjects

No patients will be withdrawn from this study without their consent.

11) Risks to Subjects

There is the potential risk of loss of confidentiality; however, for all data, only study personnel will have access to these materials. All data will be destroyed 7 years after completion of the study.

Because this specific intervention has never been tested at UC Davis (though telemedicine has been used in these emergency departments for many years for other pediatric patients), it is possible that there are unforeseen risks to the intervention. This is why monitoring the implementation outcomes are important—the study team will be closely observing the implementation for any unforeseen risks and will take immediate action if any risks are identified. Based on prior studies that have used this technology, it is highly unlikely that this intervention will cause any risk.

12) Potential Benefits to Subjects

Patients who receive a telemedicine consultation may find benefit.

13) Multi-Site Research

N/A

14) Community-Based Participatory Research

In preparation for the original proposal for this study, we conducted three meetings with community advisory boards, which laid the foundation for the study design and evaluation. For the resubmission of that proposal, we reconvened with members from each of these boards to focus more on parent/family-centered measures. Our team of clinical investigators, consortium hospital partners, as well as our two broadly representative community advisory boards, are confident that these two models of care can be effectively compared, and that the results will provide important solutions to problems facing families wanting to improve specialized trauma care for children. As highlighted in the PCORI Research Prioritization Topic Brief entitled, “Rural Trauma Care,” improving rural trauma care is a “high-impact target.”¹⁵ Recent data derived on adult patients have documented the impact that telemedicine can have on clinical outcomes in a variety of trauma settings.¹⁶⁻²¹ Having the core members of a regionalized Level I pediatric trauma center available virtually at the bedside of injured children has the potential to have a positive impact on the parent and family involvement in shared decision making, which may reduce unnecessary and financially burdensome transfers. *Alternatively, parents and families may prefer to err on the side of safety and have an injured child immediately transferred to the regional Level I pediatric trauma center, so delaying or avoiding the transfer of an injured child to a better equipped and staffed facility could result in increased parent/family distress, healthcare utilization, and out-of-pocket costs.* Hence, a rigorous comparison of the two prevailing models of care is needed to inform the choice between them.

15) Sharing of Results with Subjects

Results will not be shared with subjects.

16) Prior Approvals

N/A

17) Provisions to Protect the Privacy Interests of Subjects

All information will be kept in secure REDCap database and StudyPages.

Only members of the research team will have access to the data.

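### Does collecting transfer consultations until March 2024, ten months after the primary analyses are due, leave the transfer analysis undefined?

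*Combined protocol and SAP*

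**What the plan says.** The relevant dates are spread over three sections of the combined protocol and SAP.

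- **Section 4 (Study Timelines).** Consultations from the eligible emergency departments are abstracted "between November 30th, 2020 and March 31st, 2024". For the surveys, "They will be given until 104 days after the eligible emergency department visit to complete the final survey". On analysis, "The study team will complete primary analyses by May 31st, 2023".
- **Section 5 (Study Endpoints).** "Transfer consultation data will be collected until March 31st, 2024", and separately "Surveys will be collected until March 14th, 2023".
- **Section 6 (Procedures Involved).** "After a six-month pre-implementation period, the study will begin with all hospitals beginning in the standard of care condition", with 13 consecutive 8-week periods of enrolment. Then: "Following the 2-year (13 x 8 weeks) data collection period, there will be a six-month post-implementation period for data analysis and dissemination". Under Retrospective Data Entry, "Barton Memorial Hospital patients will be entered into REDCap dating back to 11/30/2020".

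Section 7 argues, in support of the consent waiver, that outcomes have to be assessed on every eligible consultation, and it names transfers and potentially avoidable transfers. Its data analysis plan specifies a generalized linear mixed model with hospital random effects, a time-varying VPTC indicator and a fractional polynomial in calendar date of enrolment. It states no data cut.

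**The concern.** Section 6 puts data collection at two years, followed by six months for analysis. Sections 4 and 5 let consultations run for well over three years. On the scheduled rollout every hospital is on VPTC once the 13 periods are over, so the additional consultations bring no concurrent standard-of-care patients. They could still influence the fitted calendar trend, and through it the VPTC estimate for Aim 1b.

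A reader could therefore ask whether the transfer result is final in May 2023 or could be replaced by one from the longer data set. If that were settled after both results were known, the more favourable one could be chosen.

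**Working it through.** **Inputs.** Consultation window 30 November 2020 to 31 March 2024 (sections 4 and 5); 13 periods of 8 weeks (section 6); survey close 14 March 2023 (section 5); 104 days allowed for the last survey and analysis deadline 31 May 2023 (section 4). Days are elapsed days; counting both end dates adds one.

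**The plan's own figure.** 13 × 8 × 7 = 728 days, against 730 for two years. The stated length reproduces.

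**The mismatch.**
- Consultation window: 1,217 days.
- Excess over the design: 1,217 − 728 = 489 days; 489 / 1,217 = 40%.
- 31 May 2023 to 31 March 2024: 305 days; 305 / 1,217 = 25%.

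**Do the other dates identify the 13 periods?** Suppose they start on 30 November 2020, with pre-implementation before that.
- End of the periods: 30 November 2020 + 728 days = 28 November 2022 (last enrolment day 27 November).
- Last survey due: 27 November 2022 + 104 days = 11 March 2023. Stated survey close: 14 March 2023, 3 days later.
- In reverse: 14 March 2023 − 104 days = 30 November 2022, two years after the start of the window.
- End of the six-month analysis phase: 28 November 2022 + 26 weeks = 29 May 2023. Stated deadline: 31 May 2023, 2 days later.
- The back-entry of one hospital's patients also goes to 30 November 2020.

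**The alternative starts fit poorly.**

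| Start of the 13 periods | End | Consequence |
|---|---|---|
| 30 November 2020 | 28 November 2022 | Survey close, analysis deadline and back-entry all fit |
| 29 to 31 May 2021 (six months of pre-implementation from 30 November 2020) | 27 to 29 May 2023 | Surveys close 74 to 76 days before the periods end; 2 to 4 days remain for analysis |
| 3 April 2022 | 31 March 2024 | Analysis deadline falls at week 60 of 104 |

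The second and third starts also sit badly with the back-entry passage, under which patients seen from 30 November 2020 are entered and, where their timeline allows, recruited to the surveys.

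**What this leaves open.** On the first reading the 489 later days divide into 489 − 305 = 184 before the deadline and 305 after it. The 305 days cannot contribute to an analysis completed before they occur. The 184 days fall in what section 6 describes as the analysis phase, after data collection for the comparison. An analyst following sections 4 and 6 would therefore use the 13 periods for a May 2023 contrast.

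**The case for a change.** The strongest case for a change is that this has to be inferred. Section 7's statement about evaluating every eligible consultation, read literally, cannot be met by May 2023 if consultations continue to March 2024. Nor does any section say whether transfers belong to the primary analyses due then. If the contrast were tested on the 13 periods and again on the whole window, with either result counted, type I error would exceed 5%. It would be about 6.9% with period effects and 7.9% with a linear trend, assuming 10 hospitals switching at weeks 8 to 80, 10 patients per hospital-period and an intracluster correlation of 0.05.

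The absence of period dates, a data cut and a specific role for the later consultations stands. The rest carries less weight.

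- The error figures describe a procedure that no section plans, and they rest on assumed volumes, since the documents give no consultation counts. The 7.9% also needs a linear trend, whereas section 7 selects the polynomial order from the data; quadratic to quartic trends give 6.9% to 7.0%.
- Sections 4 and 5 give surveys and consultations separate end dates. The analysis deadline is 78 days after survey close (17 + 30 + 31). A deliberately longer consultation stream is possible, and section 7 gives a general reason for abstracting all consultations. The two-year period in section 6 need not cover all abstraction.
- The March 2024 date appears in a version dated 22 September 2022, day 661 of the window on the 30 November 2020 start. That is 67 days before the 13 periods end (728 − 661) and well before the analyses are due.

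**Conclusion.** The dates do not line up fully, and the document does not explain why consultations continue to March 2024. The mismatch is 489 of 1,217 days, 305 of them after the analysis deadline. It is a minor gap in the timeline that analysts can fill sensibly, and no bias is shown.

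Both ways of filling it give a usable analysis. A May 2023 contrast rests on the 13 periods, and the remaining dates fix these to within 2 to 3 days. A later analysis on the whole window is the same stepped-wedge comparison with a longer all-VPTC tail, fitted with the hospital effects and calendar-time adjustment already specified. Writing out the period dates and the role of later consultations would be tidier, but it would correct no wrong result and supply no better method.

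This rests on three assumptions: the 13 periods began on 30 November 2020, the rollout kept to schedule, and, for an analysis on the whole window, the chosen polynomial describes the calendar trend adequately. The first is strongly supported by the other dates but is not stated.

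### Does the pledge not to use Marshall Medical Center data for research leave a listed study hospital without usable data?

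*Combined protocol and SAP*

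**What the plan says.** Section 3 (Inclusion and Exclusion Criteria) takes injured children at the time of a transfer consultation call to UC Davis "from eleven outside emergency departments". The list includes Marshall: "Adventist Health Lodi, Adventist Health Rideout, Marshall Medical Center, Mayers Memorial Hospital". Section 4 abstracts data for every consultation from those departments and makes no exception for Marshall.

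Section 6 (Procedures Involved) names one source for the system-level data: "we will abstract the following variables from the UC Davis EMR: Sending hospital". The list goes on to the outcome and time of the transfer call, the specialist who took it, Glasgow Coma Score at consultation and at departure, the admitting service, disposition, discharge and parent contact details. The design table in the same section has ten rows and is headed "One of ten hospitals is randomized to VPTC according to stratification".

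Section 7 (Data and/or Specimen Management and Confidentiality) notes that the EMR holds Marshall's clinical data as well. It then gives the undertaking "I understand that MMC patient data cannot be accessed for research purposes" and adds "I must take the necessary steps to ensure that MMC data is not accessed, used, or disclosed for UC Davis Health research purposes". Further down, the same section argues for a consent waiver on the ground that "we need to evaluate outcomes on all the eligible patient transfer consultations".

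**The concern.** The abstraction instruction and the confidentiality undertaking point at the same EMR and, read plainly, at the same children. No section defines which records count as Marshall's, cites a permission, or names another source for this hospital. The waiver argument in Sections 7 and 17 does not mention Marshall.

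Two things would be at stake. If Marshall contributed nothing, the trial would lose a whole within-hospital contrast, in a design where each hospital is its own control. If Marshall children were visible only once they reached UC Davis, ascertainment would depend on transfer, which is an Aim 1b outcome and something VPTC may change.

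**Working it through.** **1. What the undertaking covers.** Section 7 presents Marshall's data as something the EMR contains in addition to UC Davis's own. The wording is first-person and conditional. It sits beside a parallel item on student educational records, a subject that nothing else in this protocol touches. It reads as a standing institutional attestation about Marshall's own records, not as a rule written for this trial.

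**2. Outcome by outcome, if only Marshall's own records are barred.**

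| Outcome | Source for a Marshall-referred child | Does it need Marshall's own record? |
|---|---|---|
| Transfer (Aim 1b) | Outcome of the UC Davis transfer-center call (Section 6) | No; it should be recorded whether or not the child moves |
| Potentially avoidable transfer (Aim 1b) | UC Davis encounter of the transferred child | No; Section 7 treats it as a classification of transfers |
| Experience and distress (Aim 1a); costs and burden (Aim 3) | Parent-reported at 3 and 30 days | No; surveys go to parents of consulted children regardless of transfer |
| 30-day utilization (Aim 2) | No source stated | Open, but open for all hospitals |

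**3. Is Marshall different from the other hospitals?** Section 3 names eleven hospitals. Section 7 identifies only Marshall as sharing the EMR. Nothing says that the EMR holds local emergency department records for the other 11 − 1 = 10. For their children who are not transferred, local disposition, discharge and contact details would likewise be limited to what the call record holds. Barring Marshall's own records therefore treats it like the rest. Using them would give one hospital fuller follow-up than the others.

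**4. Size of the worst case.** The documents give no power calculation or cluster-period size, so there is no plan figure to reproduce. The following is an illustration. From Section 6: I = 10 hospitals, T = 13 periods, one switch per period. Assumed: first switch at the start of period 2, equal hospitals, m = 5 patients per hospital-period, categorical period effects, total variance 1. The ICC of 0.05 is a general remark in Section 6, not a design input. The Hussey–Hughes variance is

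Var = I·s²(s² + T·t²) / [(I·U − W)s² + (U² + I·T·U − T·W − I·V)t²],

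with s² = 0.95/5 = 0.19 and t² = 0.05. U is the number of VPTC cells, W the sum of squared period totals and V the sum of squared hospital totals.

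- All ten hospitals: U = 75, W = 585, V = 645. Var = 1.596 / (165 × 0.19 + 1320 × 0.05) = 1.596/97.35 = 0.01639.
- First hospital to switch removed: U = 63, W = 447, V = 501. Var = 1.4364 / (120 × 0.19 + 1020 × 0.05) = 1.4364/73.8 = 0.01946; ratio 1.187. Removing the last gives the same.
- Fifth hospital removed: U = 67, W = 463, V = 581. Var = 1.4364 / (140 × 0.19 + 1080 × 0.05) = 1.4364/80.6 = 0.01782; ratio 1.087.

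With m = 10 the ratios run from 1.178 to 1.092. Over ICC 0.01 to 0.10 and m = 2 to 10 they run from about 1.07 to 1.23. A design with 80% power would fall to Φ(2.802/√1.187 − 1.960) = 73%, or to Φ(2.802/√1.087 − 1.960) = 77%, at m = 5 and ICC 0.05. All of this applies only if Marshall supplies no data at all.

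**5. Would a clarification change a result?** A sentence limiting every hospital to transfer-center records, UC Davis encounters and surveys would confirm step 2. It would not make Aim 2 ascertainment equal: transferred children would have UC Davis encounters plus surveys, and the others surveys only.

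**The case for a change.** The strongest reply is that an undertaking in an approved protocol binds even if it is boilerplate. It names a study hospital and requires steps to keep its data out of research, and none are described. The narrow reading of Marshall's data is an inference that the text never states. Without a rule, abstractors could look up later Marshall visits for Marshall children and for no one else, or could discard Marshall children altogether. A short paragraph would prevent both.

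The silence is real, and naming the permitted sources would be good housekeeping. The consequences do not follow from it. The narrow reading lets every section be followed together, while the wide one contradicts the hospital list, the abstraction scope and the completeness argument in Section 7 itself. An abstractor who obeys the undertaking cannot over-ascertain Marshall, because its own records are closed to research. Dependence of some follow-up on transfer is a fair worry, mainly for Aim 2, but it is shared by all hospitals and the Marshall wording neither creates nor cures it. Section 6 also reports that one unnamed hospital withdrew, so Marshall's actual contribution is unknown.

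**Conclusion.** No change to the plan follows. The sections can be followed together if the bar covers Marshall's own clinical records and the study uses UC Davis transfer-center records, UC Davis encounters and parent surveys. On that reading Marshall keeps its place in the stepped wedge and is treated like the other hospitals. The 9% to 19% rise in variance describes a total loss that the text does not establish, and it rests on assumed hospital-period sizes, equal hospitals and a borrowed ICC. The conclusion assumes that the call outcome is recorded for children who are not transferred, as its place in the Section 6 variable list implies, and that the UC Davis EMR holds no local records for the other hospitals. What remains is a documentation gap of one sentence, or of a recorded permission, which analysts would fill sensibly without altering any estimate.
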